## 2 Sample Size Calculation

Based on pre-pandemic data from KPNC, the 90-day regional rate of readmission for any reason for adults hospitalized with heart failure is approximately 10-15%. Using this conservative estimate of 10% for the primary outcome of all-cause readmissions among hospitalized adults with heart failure, type 2 diabetes mellitus (hereafter referred to as diabetes) and/or chronic kidney disease who are discharged home, a total sample size of 2000 (1000 assigned to MTMs, 1000 assigned to usual care) and a two-sided  $\alpha$ =0.05 will provide 80% power to detect a hazard ratio of 0.68, corresponding to a 32% relative reduction in the risk of readmission for any cause among participants receiving MTMs versus usual care. Assuming a higher 90-day rate of 20% for a composite outcome (i.e., hospitalization, emergency department visit or death from any cause) and a two-sided  $\alpha$ =0.05, a sample size of 2000 will have 80% power to detect a hazard ratio of 0.76, corresponding to a 24% relative reduction in the risk of this composite outcome among participants receiving MTMs versus usual care.

Comparisons in utilization and survival outcomes between participants receiving MTMs alone compared with MTMs and remotely delivered nutritional counseling are considered exploratory given the limited power to detect clinically meaningful differences. However, given the anticipated total sample sizes of 2000 (1000 assigned to MTMs, 1000 assigned to usual care) or 1000 (500 assigned to MTMs alone, 500 assigned to MTMs with remotely delivered nutritional counseling) and using a two-sided  $\alpha$ =0.05, we will have >80% power to detect even small differences in patient reported outcomes which rely on continuous measures.

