#### 3.3 Covariates

Baseline characteristics overall and by treatment arm will be described using the list of covariates in **Table 3-1**. Balance of characteristics will be assessed using standardized differences. Given the potential unknown impact of one or more surges of Covid-19 during the enrollment and follow-up period of the study, an *a priori* decision was made to adjust for indices for acute severity of illness, predicted short-term readmission risk and multimorbidity burden as well as the presence of active Covid-19 during the index hospitalization, along with any observed additional baseline differences in participant characteristics for regression models of efficacy.

**Table 3-1.** List of candidate covariates.

| Category                              | Variables   |
|---------------------------------------|---|
| Demographic characteristics           | Age, self-reported gender, self-reported race/ethnicity   |
| Prior medical history                 | Heart failure, diabetes mellitus, chronic kidney disease, acute myocardial infarction, coronary artery bypass surgery, percutaneous coronary intervention, mitral or aortic valvular disease, atrial fibrillation or flutter, ventricular tachycardia or fibrillation, ischemic stroke or transient ischemic attack, venous thromboembolism, hypertension, dyslipidemia, current smoker, hospitalized bleed, hyperthyroidism, hypothyroidism, chronic liver disease, chronic lung disease, diagnosed depression, diagnosed dementia |
| Pre-admission vital signs             | Body mass index, systolic blood pressure  |
| Index hospitalization characteristics | length of stay, major discharge diagnosis category (MDC) based on diagnosis-related groups (DRG), laboratory-based acute physiology score version 2.0 (LAPS 2), predicted readmission risk score, comorbidity point score version 2.5 (COPS 2.5), evidence of active Covid-19 infection   |
| Inpatient laboratory values           | Hemoglobin, serum creatinine, blood urea nitrogen   |

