### 4 Efficacy analyses

### 4.1 Primary outcome: Readmission for any cause within 90 days post-discharge

The frequency and risk with associated 95% exact (Clopper-Pearson) binomial confidence intervals (CI) for participants experiencing readmission for any cause within 90 days after discharge from the index hospitalization will be reported by treatment arm. Risk differences will be calculated along with associated Wald 95% CI. Cumulative incidence curves from the cumulative incidence function will be reported descriptively without statistical testing.

The primary measure of association will be the hazard ratio (and associated 95% CI) for MTMs vs Usual Care obtained from a Cox proportional hazards model adjusted for acute severity of illness, predicted short-term readmission risk and multimorbidity burden as well as the presence of active Covid-19 during the index hospitalization, along with any observed additional baseline differences in participant characteristics in the primary analysis population.

The subdistribution hazard ratio (95% CI) for MTMs vs Usual care obtained from Fine and Gray subdistribution hazard models adjusted for acute severity of illness, predicted short-term readmission risk and multimorbidity burden as well as the presence of active Covid-19 during the index hospitalization, along with any observed additional baseline differences in participant characteristics in the primary analysis population will also be reported to examine the effect of MTMs on the cumulative incidence of hospitalizations for any cause accounting for the potential effects of a competing risk of death.

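### The primary Cox model adds covariates according to observed baseline imbalance, with no cutoff, decision-maker or timing, so the model cannot be written down in advance

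*SAP*

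**What the plan says.** SAP 4.1 names the estimator: "The primary measure of association will be the hazard ratio (and associated 95% CI) for MTMs vs Usual Care", taken from a Cox model. SAP 3.3 records that an a priori "decision was made to adjust for indices for acute severity of illness, predicted short-term readmission risk and multimorbidity burden", together with active Covid-19 at the index stay. Both sections then leave the rest of the model open. SAP 3.3 adds "along with any observed additional baseline differences in participant characteristics for regression models of efficacy", and SAP 4.1 repeats this for the primary model: "along with any observed additional baseline differences in participant characteristics in the primary analysis population".

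The only related instruction is in SAP 3.3: "Balance of characteristics will be assessed using standardized differences". No numeric cutoff follows. Table 3-1 is titled "List of candidate covariates", but the text does not say that additions are confined to it.

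The open clause reaches beyond the primary Cox model. SAP 4.1 repeats it for the Fine and Gray model, SAP 4.2 carries the 4.1 methods to every secondary clinical outcome, and SAP 4.4 carries them to the comparison of the two meal arms. SAP 4.3 is looser still: the patient-reported outcome (PRO) models adjust for baseline differences in that subpopulation, with no fixed covariates at all.

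**The concern.** A confirmatory model should be fully written before anyone can see how its form affects the answer. Here two competent analysts could both follow the SAP and fit different primary models, because each must decide for themselves what counts as a difference. No model with only the four fixed covariates is named, either as primary or as a sensitivity analysis, so there is no anchor to fall back on.

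Imbalance is also a weak criterion for choosing covariates. A variable improves precision, or corrects a misleading comparison, to the extent that it predicts readmission. An imbalance in a variable unrelated to readmission needs no adjustment, while a strongly prognostic variable is worth including even when balanced.

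At stake are the primary hazard ratio and its confidence interval, and the credibility of a significance claim that might hold under one reading of the clause and fail under another. There is a knock-on effect in SAP 3.4, where the choice between median and multiple imputation depends on missingness across the covariates of interest, a set that this clause leaves undefined.

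**Working it through.** The plan gives no figure for the effect of its covariate rule, so there is none to reproduce. The inputs come from the SAP.

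**Inputs**
- Arms: 1000 and 1000 (SAP 2).
- Event rate: 10% at 90 days (SAP 2), so about 200 events if applied to both arms. The approximate SE of the log hazard ratio is then 2/√200 = 0.14.
- Candidates in Table 3-1: 3 demographic + 21 history + 2 vital signs + 6 index-stay + 3 laboratory = 35. Four of the index-stay entries are the fixed covariates, leaving 31.
- Cutoff: not stated. Assumed range 0.05 to 0.20.

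**Step 1: how many covariates chance alone would add**

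Under pure randomization the SE of a standardized difference is √(2/1000) = 0.0447. For cutoff c, the chance that one variable qualifies is p = 2[1 − Φ(c/0.0447)]. The expected number is 31p, and the chance of at least one is 1 − (1 − p)^31, assuming independent variables.

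| Cutoff | p | Expected additions | P(at least one) |
|---|---|---|---|
| 0.05 | 0.264 | 8.2 | above 0.99 |
| 0.088 (p<0.05) | 0.050 | 1.55 | 0.80 |
| 0.10 | 0.0253 | 0.79 | 0.55 |
| 0.20 | 0.00001 | about 0 | 0.0002 |

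The unstated cutoff decides whether the primary model has about 4 covariates or about 4 + 8 = 12.

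**Step 2: what this does to the test**

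Cox models were simulated with 1000 per arm, about 10% events, 4 fixed and 31 candidate covariates. Assumptions: independent standard-normal covariates, log hazard ratio 0.25 per SD for each fixed covariate, and values spread from −0.255 to +0.255 per SD across the candidates. There were 3000 null trials (Monte Carlo SE about 0.4 percentage points) and 1000 trials at the design hazard ratio of 0.68.

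- Each single rule applied mechanically (no additions, 0.20, 0.10, p<0.05, 0.05, or all 31): type I error 5.0–5.6%.
- Most favourable of four readings (none, 0.10, p<0.05, 0.05) chosen after results: 6.4%. Most favourable of all six: 7.6%.
- Spread of the log hazard ratio over five readings (all except the all-31 model): median 0.03, 95th percentile about 0.08. A shift of 0.08 multiplies the hazard ratio by e^0.08 = 1.08, for example from 0.68 to 0.74.
- The significance verdict differed among those five readings in 2.5% of null trials and 8.9% of trials at hazard ratio 0.68.

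A separate linear-model approximation, with covariates explaining 5–20% of the variation, gave 6.2–6.6% for the best of five rules. In it, single cutoffs gave type I error as low as 3.4%. The Cox simulation did not show that conservatism, so it is not relied on here.

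**Step 3: is the gap closed elsewhere?**

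Protocol 11.4.3 has treatment-revealing data added after a clean file is declared and before final lock. It does not mention covariate selection, who makes it, or whether that person can see outcomes. No other section does.

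**The case against.** The strongest defence comes from the design. Patients are randomized before manual eligibility review and before consent (Protocol 6, 7.4 and 7.5), and the primary population is those who consented and survived to discharge (SAP 3.1). Differences between the analysed arms may therefore reflect selection after randomization, not only chance, so looking for imbalance and adjusting for it has a real rationale. This stands. It is a reason to keep such an adjustment somewhere in the plan, and it means the chance-only counts above may be too low. It does not excuse the missing rule: if more variables may qualify, the list should be settled sooner.

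Several stronger readings are tempting and are not supported:

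- A reader might infer that covariates will be chosen after outcomes are seen. The documents do not say so. A baseline table by arm needs allocation but not outcomes. The defect is that the order is not fixed.
- A reader might infer that imbalance-driven selection itself inflates type I error. In the Cox simulation it did not; inflation needed the rule to be picked after seeing results.
- A reader might infer a separately selected model for each population. Only the PRO wording in SAP 4.3 implies that; SAP 4.2 leaves it open for the heart failure and diabetes subpopulations.

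It is also fair that SAP 4.1 reports risks by arm and a risk difference, which need no covariates, so an unadjusted comparison will stand beside the hazard ratio. That helps a reader, but it is not the primary measure. Finally, a numeric cutoff applied blind to outcomes would remove the freedom of choice. It would still select on imbalance rather than prognosis.

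**Conclusion.** The concern holds in a limited form. Four covariates are fixed; the remainder of the primary model is open, and nothing in either document closes it before outcomes can be seen. The size is modest. The plausible readings range from about 4 to about 12 covariates, and the typical movement in the log hazard ratio (0.03) is small against its SE of about 0.14. The worst case is a type I error of roughly 6–8% instead of 5%, and it arises only if the most favourable rule is chosen after the results.

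The counts assume additions come from Table 3-1, independent covariates and pure chance imbalance. The error rates and verdict changes depend on the assumed prognostic strengths; weaker ones would shrink them. The specification gap depends on none of these assumptions. Because it affects the primary analysis and is cheap to close, it should be changed.

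**What to change.** In SAP 3.3 and 4.1, replace the open clause with a covariate set, including coding, fixed before allocation is merged with outcomes. One reasonable set is LAPS2, the predicted readmission risk score, COPS 2.5, active Covid-19, age, gender, and heart failure, diabetes and chronic kidney disease status, with the Cox model stratified by medical center, the randomization stratum in Protocol 7.4. The exact additions beyond the four are the sponsor's choice; what matters is that they are named for prognosis and in advance.

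Two adaptations are needed:
- In the heart failure and diabetes subpopulations, drop the condition indicator that is constant there.
- In SAP 4.3, replace the adjustment for baseline differences with the same set plus the baseline score of the item analysed.

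Keep adjustment for observed imbalances, including any arising from consent after randomization, as a labelled sensitivity analysis.

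The cost is a few lines of SAP text. The listed covariates are already in Table 3-1 and medical center is known from randomization, so no new data are needed. The downside is that an imbalance in an unlisted variable is handled only in the sensitivity analysis.

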### 4.2 Secondary clinical outcomes

- 1. 90-day emergency department visit for any cause
- 2. 90-day death for any cause
- 3. Composite of 90-day readmission, emergency department visit, or death for any cause
- 4. 90-day readmission for heart failure
- 5. 90-day readmission for diabetes-related complication
- 6. 60-day readmission for any cause
- 7. 30-day readmission for any cause

All analyses and reporting for the primary outcome described in Section 4.1 will also be conducted for all secondary clinical outcomes.

Analyses of emergency department visits, death and the composite outcome will be conducted in the primary analysis population. Analysis of hospitalization for heart failure will be conducted in the heart failure subpopulation only. Analysis of hospitalization for a diabetes-related complication will be conducted in the diabetes subpopulation only.

Subdistribution hazard ratios will not be calculated for all-cause death and the composite outcome of utilization and death, given that death is part of those outcomes.

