#### 4.4 Secondary comparisons

All outcome comparisons outlined in Sections 4.1 – 4.3 will be repeated in the MTMs, heart failure MTMs, diabetes MTMs, and PRO MTMs subpopulations, as appropriate. Frequencies and risks, risk differences, hazard ratios, subdistribution hazard ratios, and linear regression coefficients will be calculated and reported comparing participants assigned to MTMs alone versus assigned to MTMs with remotely delivered nutritional counseling.

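### The SAP carries the primary outcome's Wald risk-difference interval and open-ended covariate adjustment unchanged into sparse cause-specific and subset analyses, with no small-event rule (minor, conditional on event counts)

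*SAP*

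**What the plan says.** SAP 4.1 sets the methods for 90-day all-cause readmission. Each arm's risk gets an exact Clopper-Pearson interval. For the contrast, "Risk differences will be calculated along with associated Wald 95% CI". The main estimate comes from a "Cox proportional hazards model adjusted for acute severity of illness, predicted short-term readmission risk and multimorbidity burden", plus active Covid-19, "along with any observed additional baseline differences in participant characteristics in the primary analysis population". A Fine-Gray model uses the same adjustment.

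SAP 4.2 then says "All analyses and reporting for the primary outcome described in Section 4.1 will also be conducted for all secondary clinical outcomes". The one modelling exception is that death and the composite get no subdistribution hazard ratio. Heart failure readmission is analysed only in the heart failure subpopulation, and diabetes-complication readmission only in the diabetes subpopulation. SAP 4.4 adds that all comparisons "will be repeated in the MTMs, heart failure MTMs, diabetes MTMs, and PRO MTMs subpopulations", where appropriate.

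SAP 3.3 describes the data-driven part as "along with any observed additional baseline differences in participant characteristics for regression models of efficacy", and says "Balance of characteristics will be assessed using standardized differences". It gives no cut-off for a difference and no limit on how many covariates may enter. Neither document gives a minimum event count, a sparse-data method or a rule for a model that fails.

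**The concern.** The 4.1 methods suit about 10% risk in 1000 versus 1000 participants. Cause-specific readmission in a disease subpopulation, and above all in its meal-arm half, may yield only a handful of events. Two things can then go wrong. The Wald interval for a risk difference relies on a large-sample approximation that fails with very few events. And chance imbalances become more frequent as the sample shrinks, so if balance is re-judged in each subset, the models with the fewest events receive the most covariates.

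The heart failure and diabetes readmission comparisons against usual care belong to Aim 2, and the counseling comparison to Aim 4. Without a stated rule, the response to a sparse or failed model would be chosen after the data are seen.

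**Working it through.** **Inputs from the documents.** SAP 2: 1000 vs 1000 for meals against usual care, 500 vs 500 within the meal arms, 10% primary rate, 20% composite rate, hazard ratio (HR) 0.68. SAP Table 3-1: 35 candidate variables by my count, 4 of them prespecified, leaving 31.

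**Assumptions, not in the documents.** Imbalance cut-off |standardized difference| > 0.1; independent candidates; Covid-19 prevalence 8-10%; rare-outcome risks 0.5-2%; subset sizes 150-350 per arm.

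**The plan's own figure.** Schoenfeld events for HR 0.68 at 80% power: 4 × (1.960 + 0.842)² / (ln 0.68)² ≈ 212. A 10% usual-care rate gives 100 + 1000 × (1 − 0.9^0.68) ≈ 169 events and 70.8% power. A 10% pooled rate gives 200 events and 77.9%, a near miss. Either way the primary model has well over 100 events for about 6 parameters, so the present point does not touch it.

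**1. Covariates flagged by chance.** Expected number = 31 × 2 × [1 − Φ(0.1 / √(2/n))], n per arm. Parameters = treatment + 4 fixed + flagged.

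| n per arm | P(flag) | Expected flags | Parameters |
|---|---|---|---|
| 1000 | 0.025 | 0.8 | 6 |
| 500 | 0.114 | 3.5 | 8-9 |
| 350 | 0.186 | 5.8 | 11 |
| 250 | 0.264 | 8.2 | 13 |
| 150 | 0.387 | 12.0 | 17 |

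At 150 per arm, risks of 1-5% give 3-15 events, fewer than the 17 parameters. In 2000 patients, risks of 1-3% give 20-60 events for about 6 parameters.

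**2. Effect on the treatment hazard ratio (simulation, 200-500 runs per setting).**
- 1000 per arm, 2% risk, about 35 events: no failures with 0 to 20 adjusters. The ratio of upper to lower confidence limit is 3.9-4.0 throughout.
- 500 per arm, 2%, about 17-18 events: limit ratio 7.2-7.5 whatever the number of adjusters.
- 350 per arm at 1% (11 parameters) and 250 per arm at 2% (13 parameters): variance of the log HR 19% to 41% above a one-covariate model, depending on the assumed prognostic effects.
- 150 per arm, 2%, about 5 events: HR unusable in 13% of runs unadjusted, 14% with 4 adjusters, 22% with 12 and 50% with 20. The expected 16 adjusters (4 + 12) lie between the last two.
- With the four fixed covariates only, the variance penalty at 250-350 per arm is about 3-6%.

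The Covid-19 flag explains most non-convergence. At 8% prevalence and no association with outcome, the chance of no Covid-19-positive event is 0.92^7 = 0.56 with 7 events and 0.92^10 = 0.43 with 10. That coefficient then has no finite estimate. With the four fixed covariates, the treatment coefficient stayed finite whenever both arms had an event.

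**3. Risk-difference interval (exact binomial enumeration).**

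| n per arm | Risks | Expected events | Wald | Newcombe |
|---|---|---|---|---|
| 150 | 0.5% vs 1.0% | 2.25 | 88.4% | 99.6% |
| 150 | 0.5% vs 1.5% | 3.0 | 89.1% | 99.2% |
| 250 | 0.5% vs 1.0% | 3.75 | 90.5% | 99.2% |
| 250 | 0.5% vs 1.5% | 5.0 | 93.2% | 97.6% |
| 350 | 0.5% vs 1.0% | 5.25 | 94.4% | 97.6% |
| 500 | 0.5% vs 1.0% | 7.5 | 94.0% | 96.5% |
| 150 | 1.0% vs 1.0% | 3.0 | 97.1% | 99.1% |
| 250 | 1.0% vs 1.0% | 5.0 | 95.5% | 97.6% |

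The expected event count matters more than the sample size: 0.34% vs 0.5% at 500 per arm (4.2 events) gives Wald 92.9%.

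**The case against.** Four objections carry weight.

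**Where imbalance is judged.** SAP 4.1 ties the extra covariates to differences "along with any observed additional baseline differences in participant characteristics in the primary analysis population". Read naturally, balance is assessed once at 1000 per arm, which adds about 0.8 covariates, and the larger variance losses disappear. This largely stands. But 4.3 judges baseline differences within the patient-reported-outcome subset and 4.4 is silent for the others, so the text should say which applies.

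**False positives.** A reader might infer that Wald intervals will exclude zero too often. The documents and the arithmetic do not support that. For equal risks of 0.5-2% and 150-500 per arm, Wald coverage is nominal or conservative. The striking case of 0 vs 4 events at 350 per arm (Wald 0.03% to 2.26%, Fisher p = 0.124) does not prove it either: the Miettinen-Nurminen interval also excludes zero (0.05% to 2.90%). Newcombe does not (−0.15% to 2.90%). What remains is under-coverage when risks differ and events are very few.

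**Non-convergence.** A reader might take warning-flagged fits as lost treatment estimates. With the four fixed covariates, what diverges is a nuisance coefficient. No covariate rule repairs an arm with no events, and few events remain the main limit on precision.

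**Status.** SAP 2 calls the utilization and survival comparisons between the two meal arms exploratory, and 4.4 is qualified by appropriateness. That lowers the stakes there. It does not cover heart failure and diabetes readmission against usual care, and the qualifier states no criterion.

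**Conclusion.** The concern holds in a limited form and is minor. The SAP does copy a large-sample interval and an uncapped covariate rule into analyses that may be very sparse, with no fallback. Wald coverage falls to 88-93% only with about five or fewer expected events in total and unequal risks. Adjustment inflates the variance of the treatment log HR by roughly 20-40% at 250-350 per arm, and makes it inestimable in some runs at 150, only if imbalance is re-judged within each subset.

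It would be tempting to say that every secondary outcome is affected. That is not shown: death in the full 2000-patient population, the composite, emergency department visits and 30- and 60-day readmission have enough events under the assumptions above, or need not be rare. The sizes rest on assumed event rates, subset sizes, an imbalance cut-off and a Covid-19 prevalence that neither document states.

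**What to change.** 1. In SAP 4.1, 4.2 and 4.4, replace the Wald risk-difference interval by a Newcombe score interval. Cost: slightly wider, and conservative when events are very few.
2. For the cause-specific outcomes and all clinical-outcome models in 4.4, adjust only for the four prespecified covariates and add none chosen by observed imbalance. Cost: chance imbalances in sparse subsets go unadjusted. Dropping any of the four is not recommended, since SAP 3.3 justifies them in advance by possible Covid-19 surges and keeping them costs little precision.
3. Where an arm or a covariate level has no events, report the Cox hazard ratio from Firth's penalized likelihood with a profile-likelihood interval. State also what is reported for the Fine-Gray model in that case, because this step covers the Cox model only.

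The primary and composite Cox models stay as they are. The work is SAP wording and analysis options, with no new data.
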